11.6 Appendix 6. Sample Storage and Destruction

Any blood, bone marrow, or saliva sample collected according to the Schedule of Activities (Section 1.3) can be analyzed for any of the tests outlined in the protocol and for any tests necessary to minimize risks to study subjects. This includes testing to ensure analytical methods produce reliable and valid data throughout the course of the study. This can also include, but is not limited to, investigation of unexpected results, incurred sample reanalysis, and analyses for method transfer and comparability.

All samples and associated results will be coded prior to being shipped from the site for analysis or storage. Samples will be tracked using a unique identifier that is assigned to the samples for the study. Results are stored in a secure database to ensure confidentiality.

If informed consent is provided by the subject, Amgen can do additional testing on remaining samples (ie, residual and back-up) to investigate and better understand the leukemia disease state, the dose response and/or prediction of response to AMG 330 in combination with pembrolizumab, and characterize aspects of the molecule (eg, mechanism of action/target, metabolites). Results from this analysis are to be documented and maintained, but are not necessarily reported as part of this study. Samples can be retained for up to 20 years.

Since the evaluations are not expected to benefit the subject directly or to alter the treatment course, the results of [REDACTED] or other exploratory studies are not placed in the subject's medical record and are not to be made available to the subject, members of the family, the personal physician, or other third parties, except as specified in the informed consent.

The subject retains the right to request that the sample material be destroyed by contacting the investigator. Following the request from the subject, the investigator is to provide the sponsor with the required study and subject number so that any remaining samples and any other components from the cells can be located and destroyed. Samples will be destroyed once all protocol-defined procedures are completed. However, information collected from samples prior to the request for destruction, will be retained by Amgen.

The sponsor is the exclusive owner of any data, discoveries, or derivative materials from the sample materials and is responsible for the destruction of the sample(s) at the request of the subject through the investigator, at the end of the storage period, or as

appropriate (eg, the scientific rationale for experimentation with a certain sample type no longer justifies keeping the sample). If a commercial product is developed from this research project, the sponsor owns the commercial product. The subject has no commercial rights to such product and has no commercial rights to the data, information, discoveries, or derivative materials gained or produced from the sample. See [Section 11.3](#) for subject confidentiality.

Approved

11.7 Appendix 7. Hepatotoxicity Stopping Rules: Suggested Actions and Follow-up Assessments and Study Treatment Rechallenge Guidelines

Subjects with abnormal hepatic laboratory values (ie, alkaline phosphatase [ALP], aspartate aminotransferase [AST], alanine aminotransferase [ALT], total bilirubin [TBL]) and/or international normalized ratio (INR) and/or signs/symptoms of hepatitis (as described below) may meet the criteria for withholding or permanent discontinuation of Amgen investigational product or other protocol-required therapies, as specified in the *Guidance for Industry Drug-Induced Liver Injury: Premarketing Clinical Evaluation, July 2009*.

Criteria for Withholding and/or Permanent Discontinuation of Amgen Investigational Product and Other Protocol-required Therapies Due to Potential Hepatotoxicity

The following stopping and/or withholding rules apply to subjects for whom another cause of their changes in liver [REDACTED] (TBL, INR and transaminases) has not been identified.

Important alternative causes for elevated AST/ALT and/or TBL values include, but are not limited to:

- Hepatobiliary tract disease
- Viral hepatitis (eg, hepatitis A/B/C/D/E, Epstein-Barr Virus, cytomegalovirus, herpes simplex virus, varicella, toxoplasmosis, and parvovirus)
- Right sided heart failure, hypotension or any cause of hypoxia to the liver causing ischemia
- Exposure to hepatotoxic agents/drugs or hepatotoxins, including herbal and dietary supplements, plants and mushrooms
- Heritable disorders causing impaired glucuronidation (eg, Gilbert's syndrome, Crigler-Najjar syndrome) and drugs that inhibit bilirubin glucuronidation (eg, indinavir, atazanavir)
- Alpha-one antitrypsin deficiency
- Alcoholic hepatitis
- Autoimmune hepatitis
- Wilson's disease and hemochromatosis
- Nonalcoholic fatty liver disease including steatohepatitis
- Non-hepatic causes (eg, rhabdomylosis, hemolysis)

If investigational product(s) is/are withheld, the subject is to be followed for possible drug induced liver injury (DILI) according to recommendations in the last section of this appendix.

Rechallenge may be considered if an alternative cause for impaired liver tests (ALT, AST, ALP) and/or elevated TBL, is discovered and the laboratory abnormalities resolve to normal or baseline (see next section in this appendix).

Table 11-2. Conditions for Withholding and/or Permanent Discontinuation of Amgen Investigational Product and Other Protocol-required Therapies Due to Potential Hepatotoxicity

Analyte	Temporary Withholding	Permanent Discontinuation
TBL	> 3x ULN at any time	> 2x ULN OR
INR	--	> 1.5x (for subjects not on anticoagulation therapy) AND
AST/ALT	> 8x ULN at any time > 5x ULN but < 8x ULN for \geq 2 weeks > 5x ULN but < 8x ULN and unable to adhere to enhanced monitoring schedule > 3x ULN with clinical signs or symptoms that are consistent with hepatitis (such as right upper quadrant pain/tenderness, fever, nausea, vomiting, and jaundice)	In the presence of no important alternative causes for elevated AST/ALT and/or TBL values > 3x ULN (when baseline was < ULN)
ALP	> 8x ULN at any time	--

ALP = alkaline phosphatase; ALT = alanine aminotransferase; AST = aspartate aminotransferase; INR = international normalized ratio; TBL = total bilirubin; ULN = upper limit of normal

Criteria for Rechallenge of Amgen Investigational Product and Other Protocol-required Therapies After Potential Hepatotoxicity

The decision to rechallenge the subject is to be discussed and agreed upon unanimously by the subject, investigator, and Amgen.

If signs or symptoms recur with rechallenge, then Amgen investigational product and/or other protocol-required therapies is to be permanently discontinued. Subjects who clearly meet the criteria for permanent discontinuation (as described in [Table 11-2](#)) are never to be rechallenged.

Drug-induced Liver Injury Reporting and Additional Assessments

Reporting

To facilitate appropriate monitoring for signals of DILI, cases of concurrent AST or ALT and TBL and/or INR elevation, according to the criteria specified in the above, require the following:

- The event is to be reported to Amgen as a serious adverse event within 24 hours of discovery or notification of the event (ie, before additional etiologic investigations have been concluded)
- The appropriate CRF (eg, Event CRF) that captures information necessary to facilitate the evaluation of treatment-emergent liver abnormalities is to be completed and sent to Amgen

Other events of hepatotoxicity and potential DILI are to be reported as serious adverse events if they meet the criteria for a serious adverse event defined in [Section 11.4](#).

Additional Clinical Assessments and Observation

All subjects in whom investigational product(s) or protocol-required therapies is/are withheld (either permanently or conditionally) due to potential DILI as specified in [Table 11-2](#) or who experience AST or ALT elevations $> 3 \times$ upper limit of normal (ULN) or 2-fold increases above baseline values for subjects with elevated values before drug are to undergo a period of “close observation” until abnormalities return to normal or to the subject’s baseline levels.

Assessments that are to be performed during this period include:

- Repeat AST, ALT, ALP, bilirubin (BIL) (total and direct), and INR within 24 hours
- In cases of TBL $> 2 \times$ ULN or INR > 1.5 , retesting of liver tests, BIL (total and direct), and INR is to be performed every 24 hours until laboratory abnormalities improve

Testing frequency of the above laboratory tests may decrease if the abnormalities stabilize or the investigational product(s) or protocol-required therapies has/have been discontinued AND the subject is asymptomatic.

Initiate investigation of alternative causes for elevated AST or ALT and/or elevated TBL.

The following are to be considered depending on the clinical situation:

- Complete blood count with differential to assess for eosinophilia
- Serum total immunoglobulin (Ig)G, anti-nuclear antibody anti-smooth muscle antibody, and liver kidney microsomal antibody-1 to assess for autoimmune hepatitis
- Serum acetaminophen (paracetamol) levels
- A more detailed history of:

Approved

- Prior and/or concurrent diseases or illness
- Exposure to environmental and/or industrial chemical agents
- Symptoms (if applicable) including right upper quadrant pain, hypersensitivity-type reactions, fatigue, nausea, vomiting and fever
- Prior and/or concurrent use of alcohol, recreational drugs and special diets
- Concomitant use of medications (including non-prescription medicines and herbal and dietary supplements), plants, and mushrooms
- Viral serologies
- Creatine phosphokinase, haptoglobin, lactate dehydrogenase and peripheral blood smear
- Appropriate liver imaging if clinically indicated
- Appropriate blood sampling for pharmacokinetic analysis if this has not already been collected
- Hepatology consult (liver biopsy may be considered in consultation with a hepatologist)

Follow the subject and the laboratory tests (ALT, AST, TBL, INR) until all laboratory abnormalities return to baseline or normal or considered stable by the investigator. The “close observation period” is to continue for a minimum of 4 weeks after discontinuation of all investigational product(s) and protocol-required therapies.

The potential DILI event and additional information such as medical history, concomitant medications and laboratory results must be captured in the corresponding CRFs.

Approved

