5.1 Inclusion Criteria

Subjects are eligible to be included in the study only if all of the following criteria apply:

- 101 Subject has provided informed consent prior to initiation of any study specific activities/procedures.
- 102 Age \geq 18 years on day of signing informed consent.
- 103 AML as defined by the WHO Classification ([Section 11.10](#)) persisting or recurring following 1 or more treatment courses. Exception: promyelocytic leukemia (APML) is excluded from the study.

104 More than 5% blasts in bone marrow.

105 Eastern Cooperative Oncology Group (ECOG, [Section 11.9](#)) Performance Status of ≤ 1 .

106 Have adequate organ function as defined in [Table 5-1](#). Specimens must be collected within 14 days prior to study day 1.

Table 5-1. Adequate Organ Function Laboratory Values

System	Laboratory Value
Renal	
Measured or calculated ^a creatinine clearance (GFR can also be used in place of creatinine or CrCl)	≥ 30 mL/min for participant with creatinine levels $> 1.5 \times$ institutional ULN
Hepatic	
Total bilirubin	$\leq 1.5 \times$ ULN OR direct bilirubin \leq ULN for participants with total bilirubin levels $> 1.5 \times$ ULN
AST (SGOT) and ALT (SGPT)	$\leq 2.5 \times$ ULN
Coagulation	
International normalized ratio (INR) OR prothrombin time (PT) Activated partial thromboplastin time (aPTT)	$\leq 1.5 \times$ ULN unless participant is receiving anticoagulant therapy as long as PT or aPTT is within therapeutic range of intended use of anticoagulants
ALT (SGPT) = alanine aminotransferase (serum glutamic pyruvic transaminase); AST (SGOT) = aspartate aminotransferase (serum glutamic oxaloacetic transaminase); GFR = glomerular filtration rate; ULN = upper limit of normal. ^a Creatinine clearance (CrCl) should be calculated per institutional standard. Note: This table includes eligibility-defining laboratory value requirements for treatment; laboratory value requirements should be adapted according to local regulations and guidelines for the administration of specific chemotherapies.	

107 A male participant must agree to use contraception during the treatment period and for at least 120 days after receiving the last dose of study drug (AMG 330 or pembrolizumab).

- Acceptable methods of highly effective birth control include sexual abstinence; vasectomy; or a condom with spermicide (men) in combination with hormonal birth control or intrauterine device (IUD) (women).
- Males will not be allowed to donate sperm during this period.

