
AE = adverse event; ALT = alanine aminotransferase; AST = aspartate aminotransferase; CTCAE = Common Terminology Criteria for Adverse Events; GI = gastrointestinal; irAE = immune-related adverse event; IV = intravenous; ULN = upper limit of normal
 
^a AST/ALT: > 3.0 - 5.0 x ULN if baseline normal; > 3.0 - 5.0 x baseline, if baseline abnormal; bilirubin: > 1.5 - 3.0 x ULN if baseline normal; > 1.5 - 3.0 x baseline if baseline abnormal
 
^b AST/ALT: > 5.0 to 20.0 x ULN, if baseline normal; > 5.0 - 20.0 x baseline, if baseline abnormal; bilirubin: > 3.0 - 10.0 x ULN if baseline normal; > 3.0 - 10.0 x baseline if baseline abnormal
 
^c AST/ALT: > 20.0 x ULN, if baseline normal; > 20.0 x baseline, if baseline abnormal; bilirubin: > 10.0 x ULN if baseline normal; > 10.0 x baseline if baseline abnormal
 
^d The decision to withhold or permanently discontinue pembrolizumab is at the discretion of the investigator or treating physician. If control achieved or ≤ grade 2, pembrolizumab may be resumed.
 
^e Events that require discontinuation include but are not limited to: Guillain-Barre Syndrome, encephalitis, Stevens-Johnson Syndrome and toxic epidermal necrolysis.
				

Pembrolizumab may cause severe or life-threatening infusion-reactions including severe hypersensitivity or anaphylaxis. Signs and symptoms usually develop during or shortly after drug infusion and generally resolve completely within 24 hours of completion of infusion ([Pembrolizumab Investigator's Brochure](#)). Dose modification and toxicity management guidelines on pembrolizumab associated infusion reaction are provided in [Table 6-4](#).

Table 6-4. Pembrolizumab Infusion Reaction Dose Modification and Treatment Guidelines

NCI CTCAE Grade	Treatment	Premedication at Subsequent Dosing
Grade 1 Mild reaction; infusion interruption not indicated; intervention not indicated	
 Increase monitoring of vital signs as medically indicated until the participant is deemed medically stable in the opinion of the investigator. 	None

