8.2.5.1.4 Pembrolizumab Events of Clinical Interest (ECI)

Selected non-serious and serious adverse events are also known as Events of Clinical Interest (ECI) and must be reported to the Sponsor. Refer to [Section 8.2.5.1.2](#) and

8.2.5.1.3 for the required reporting period and the reporting requirements for non-serious and serious ECIs.

- an overdose of pembrolizumab, as defined in [Section 6.1.1.4](#)
- an elevated AST or ALT lab value that is greater than or equal to 3 x ULN and an elevated total bilirubin lab value that is greater than or equal to 2 x ULN and, at the same time, an alkaline phosphatase lab value that is less than 2 x ULN, as determined by way of protocol-specified laboratory testing or unscheduled laboratory testing.*

*Note: These criteria are based upon available regulatory guidance documents. The purpose of the criteria is to specify a threshold of abnormal hepatic tests that may require an additional evaluation for an underlying etiology. The trial site guidance for assessment and follow up of these criteria can be made available. It may also be appropriate to conduct additional evaluation for an underlying etiology in the setting of abnormalities of liver blood tests including AST, ALT, bilirubin, and alkaline phosphatase that do not meet the criteria noted above. In these cases, the decision to proceed with additional evaluation will be made through consultation between the study investigators and the Sponsor. However, abnormalities of liver blood tests that do not meet the criteria noted above are not ECIs for this study.

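### A transaminase at or above ULN at entry cannot trigger Table 11-2's permanent liver stop, although eligibility admits AST/ALT up to 2.5 x ULN

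*Protocol*

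**What the plan says.** Eligibility (Protocol Section 5.1, Table 5-1) sets the limit for "AST (SGOT) and ALT (SGPT") at 2.5 x ULN, so subjects can start treatment with raised transaminases.

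Appendix 7 (Section 11.7), Table 11-2, gives one rule for permanent discontinuation. It requires total bilirubin above 2 x ULN, or INR above 1.5x off anticoagulation, and in addition AST/ALT "> 3x ULN (when baseline was < ULN") with no important alternative cause. No AST/ALT limit is given for a baseline at or above ULN.

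Two further provisions depend on that rule:
- The absolute bar on rechallenge covers "Subjects who clearly meet the criteria for permanent discontinuation".
- The 24-hour SAE report covers "cases of concurrent AST or ALT and TBL and/or INR elevation, according to the criteria specified in the above".

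Elsewhere the protocol does provide for raised baselines. Close observation in Appendix 7 is also triggered by "2-fold increases above baseline values for subjects with elevated values before drug". Table 6-3, footnote a, defines grade 2 AST/ALT as "> 3.0 - 5.0 x baseline, if baseline abnormal".

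**The concern.** The same unexplained combined elevation permanently stops AMG 330 in a subject who started with normal enzymes, but not in one whose rising enzyme was already raised at entry. For the second subject, stopping depends on rules written for other purposes, or on judgment.

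Those other rules are also harder to reach. Where they depend on AST/ALT grade, an abnormal baseline raises the absolute level at which they act. A raised baseline thus removes the permanent stop and also delays part of the backup. The protocol itself expects that checkpoint blockade may aggravate CRS, whose listed manifestations include transaminitis and hyperbilirubinemia, so liver rules are likely to be used. What is at stake is subject safety rather than the validity of an estimate.

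**Working it through.** The documents give no figure to reproduce. The check is logical, with arithmetic on the limits.

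**Rule as written.** Stop if (TBL > 2 x ULN or INR > 1.5) and (AST/ALT > 3 x ULN and baseline < ULN) and no alternative cause. Let b be the entry value of the rising enzyme in multiples of ULN. Table 5-1 allows b up to 2.5. For b from 1.0 to 2.5 the baseline condition is false, so the rule is false through that enzyme at every later AST/ALT, TBL and INR.

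**What else in Table 11-2 acts.** Withholding has no baseline condition. It needs one of:
- AST/ALT > 8 x ULN;
- AST/ALT > 5 to < 8 x ULN for at least 2 weeks, or without enhanced monitoring;
- AST/ALT > 3 x ULN with hepatitis symptoms;
- TBL > 3 x ULN, or ALP > 8 x ULN.

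It has no INR entry. AST/ALT > 3 to 5 x ULN without symptoms, or > 5 to < 8 x ULN for under 2 weeks with monitoring, is therefore not withheld.

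**Where AST/ALT grading starts.** By Table 6-3, grade 2 starts above 3.0 x ULN from a normal baseline and above 3.0 x baseline, that is 3b x ULN, from an abnormal one. The whole > 3 to 5 x ULN range stays below grade 2 once 3b ≥ 5, that is b ≥ 5/3 = 1.67.

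| b (x ULN) | Permanent stop now, this enzyme | Grade 2 starts above (x ULN) | Added line with 2x: max(3, 2b) | Added line with 3x: max(3, 3b) |
|---|---|---|---|---|
| 1.0 | none | 3.0 | 3.0 | 3.0 |
| 1.5 | none | 4.5 | 3.0 | 4.5 |
| 2.0 | none | 6.0 | 4.0 | 6.0 |
| 2.5 | none | 7.5 | 5.0 | 7.5 |

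**Example.** AST 1.5 x ULN at entry, then 4 x ULN with INR 1.8, normal bilirubin, no anticoagulant, no symptoms, no alternative cause, not CRS; ALT does not exceed 3 x ULN.
- From a baseline below ULN: permanent stop, taking the limit as INR 1.5.
- From 1.5 x ULN: no permanent stop and no Table 11-2 withholding.
- Relative rise: 4 / 1.5 = 2.67 x baseline. Grade 2 starts above 3.0 x 1.5 = 4.5 x ULN and grade 3 above 5.0 x 1.5 = 7.5 x ULN. AST alone therefore triggers neither Table 6-3 withholding of pembrolizumab nor the grade 3–4 DLT criterion.
- The Event of Clinical Interest needs "an elevated AST or ALT lab value that is greater than or equal to 3 x ULN" together with bilirubin ≥ 2 x ULN and ALP < 2 x ULN. It is not met.
- Close observation applies, with retesting every 24 hours because INR exceeds 1.5. Investigator judgment remains.

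**The bilirubin route.** TBL > 2 to 3 x ULN lies within Table 6-3's grade 2 range of > 1.5 to 3.0 x ULN when baseline bilirubin is normal, whatever the AST/ALT baseline. That withholds pembrolizumab. Section 6.2.2.1 interrupts AMG 330 if the event requires dose modification and allows restart only at grade ≤ 1. The Event of Clinical Interest is also reportable if ALP is below 2 x ULN. This route is partly covered.

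**The case against.** The strongest reply has five parts.

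**Other rules protect these subjects.** This is largely true. Besides those above, there are the grade 2 CRS 7-day limit, the grade 4 rule, the 21-day interruption limit and discretionary discontinuation. A reader might infer that anyone entering with a raised transaminase can never be stopped for liver injury, or that the bilirubin and INR routes are equally open. The documents support neither. Table 11-2 does not say how baseline is judged when only one enzyme is raised, so a subject may still qualify through the normal one; and the bilirubin route has the cover described above. The INR route with normal bilirubin has the least.

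**Losing the rechallenge bar matters little.** For a subject already withheld, this mostly stands. "Rechallenge may be considered if an alternative cause for impaired liver tests" is followed by a requirement that the laboratory values resolve, and the subject, investigator and sponsor must all agree. In the clearest gap, however, AMG 330 is never withheld under Table 11-2, so those limits do not come into play.

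**The INR example is sensitive.** Table 11-2 prints the limit as 1.5x, while the Appendix 7 retesting text uses INR > 1.5. If it means a multiple of ULN and ULN is assumed to be 1.1 to 1.2, the limit is 1.65 to 1.8, and INR 1.8 does not exceed the upper end. A higher INR restores the example. The INR's own grade is not given; if it required dose modification, AMG 330 would be interrupted.

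**The reporting text may be wider.** If the criteria it refers to include the withholding limits, some of these subjects are covered. Other hepatotoxicity is still an SAE when it meets the general definition.

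**This is clinical judgment.** The appendix calls its actions suggested and assigns close observation to raised baselines. That supports leaving the multiple to the clinical team. It does not explain why the permanent stop has no line for baselines that eligibility admits.

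**Conclusion.** The point holds for the enzyme that was at or above ULN at entry: it cannot trigger the permanent stop or the rechallenge bar and, on the natural reading, cannot trigger the 24-hour report. Following the table exactly gives less protection to subjects who start with raised enzymes.

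The practical size is small. The documents give no frequency of raised baselines. With about 20 subjects, and an event that must also be unexplained, asymptomatic and not CRS, few are likely to be affected. This is a cheap improvement, not a defect that undermines the trial.

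The conclusion rests on three readings. First, the permanent rule is a combined one. Treating TBL > 2 x ULN alone as sufficient would conflict with withholding that starts only above 3 x ULN and with the reporting text on concurrent elevation. Second, Table 6-3's grade limits, which it labels CTCAE v5.0, also apply to the other grade-based rules. Third, the INR limit is taken as 1.5, as in the retesting text.

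**What to change.** In the AST/ALT permanent-discontinuation cell of Table 11-2 add, judged per enzyme: *or, when baseline was ≥ ULN, > 3x ULN and > [2x] baseline*. State that the rechallenge bar and the 24-hour SAE report apply to this line as well.

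The clinical team should confirm the multiple. A 2x multiple follows the close-observation trigger and catches the example (4 exceeds max(3, 2 x 1.5) = 3.0). It can also act early: from 1.5 x ULN, a value of 3.1 x ULN is 3.1 / 1.5 = 2.07 x baseline and would stop treatment if the INR or bilirubin condition were met. A 3x multiple follows Table 6-3's grade 2 limit but leaves part of the gap open, including the example (4 is below 4.5). Simply deleting the baseline condition would over-stop: from 2.5 x ULN, a value of 3.1 x ULN is only 3.1 / 2.5 = 1.24 x baseline.

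Cost: one table line and one sentence in the next amendment, and a few more permanent stops in subjects with raised baselines.
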